12.2 SIGNIFICANCE LEVEL

Significance is defined at the p<0.05 level based on a two-sided test.

12.3 TOLERABILITY ASSESSMENT

Subjects who discontinue will be queried as to any side effects experienced by the study products. The tolerability endpoint is the investigator-assessed absence of skin irritation from the facial study device at any time during the 12-week study.

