4. STUDY OBJECTIVE

The objective of this study is demonstrate the safety and efficacy of a novel direct current device in the treatment of mild to moderate inflammatory acne after 12 weeks of every other day use.

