7.1.5 STUDY MATERIAL ADMINISTRATION

All subjects will use the active ZIIP device as currently marketed. The ZIIP Device will be customized for the delivery of acne treatment with -400 microamps direct current, applied 3 days per week on non-consecutive days, on each facial zone afflicted by acne. A electroconductive media will be applied to each facial zone afflicted by acne prior to initiation of the device treatment.

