9.1 COMPLETED, DISCONTINUED OR INCOMPLETE SUBJECTS

A completed subject is a subject who has satisfied all study entry criteria and completed the 12-week study. For any subject who has started study and terminated from the study prematurely, every effort will be made to obtain final evaluations of clinical status. Reasonable effort will be made to contact any subject lost to follow-up during the course of the study in order to complete assessments and retrieve any outstanding data and clinical supplies. The investigator will choose the description that best describes the status of the subject at termination.

1. Subject completed the 12 week study period

OR INCOMPLETE/DISCONTINUED DUE TO:

- 2. Contact dermatitis
- 3. Adverse experience
- 4. Serious adverse experience
- 5. Pregnancy
- 6. Protocol violation
- 7. Subject withdrew consent
- 8. Subject lost due to follow-up issues (e.g., attendance issues)
- 9. Other (provide reason)

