10. STUDY PRODUCTS & ADMINISTRATION

10.1 FORMULATIONS

The study will consist of the ZIIP device programmed for the treatment of acne and the electroconductive media

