10.5 STORAGE AND ACCOUNTABILITY OF STUDY PRODUCT

The study product will be stored at room temperature, away from sunlight, in a locked, limited access area at the study site. Access to the study product will be limited to the investigator and staff members designated to dispense study medication. A study product log will be used to record the dispensation and return of all study products. The subject number/initials, and the initials and date of the person dispensing and receiving the returned study product will be documented on this form.

10.6

CODE DISCLOSURE

The study coordinator will not develop a code as all subjects will use the active device and electroconductive media in this monadic study.

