12.5 EFFICACY ASSESSMENT

The efficacy endpoint is the investigator assessed improvement in investigator global assessment (IGA) after 12 weeks of every other day device use as compared to baseline.

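### The tolerability endpoint counts only irritation from the device, although every subject uses the device and the electroconductive medium together and the design cannot separate the two

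*Combined protocol and SAP*

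**What the plan says.** Section 10.1 describes what is studied as a pair: "The study will consist of the ZIIP device programmed for the treatment of acne and the electroconductive media". Section 10.6 (Code Disclosure) confirms that there is no other arm: "all subjects will use the active device and electroconductive media in this monadic study". Section 7.1.5 sets the order of use: "A electroconductive media will be applied to each facial zone afflicted by acne prior to initiation of the device treatment".

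The tolerability endpoint, given in the synopsis and again in section 12.3, names one member of the pair: "The tolerability endpoint is the investigator-assessed absence of skin irritation from the facial study device at any time during the 12-week study". The sentence just before it in section 12.3 has discontinuing subjects asked about side effects of the study products, in the plural.

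The objective in section 4 is to "demonstrate the safety and efficacy of a novel direct current device in the treatment of mild to moderate inflammatory acne". The efficacy endpoint in section 12.5 is "investigator assessed improvement in investigator global assessment (IGA) after 12 weeks of every other day device use as compared to baseline". Neither mentions the medium.

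Section 9.1 lists "Contact dermatitis" as a reason for discontinuation, separate from adverse experience, and does not say which product is meant.

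**The concern.** The word *from* in the tolerability endpoint asks for a causal judgement: was this irritation due to the device or to something else? The most obvious something else is the medium, which touches the same skin at the same session. The judgement is made by an investigator who knows that everyone is on active treatment, and no rule guides it.

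On the literal wording, a subject with irritation or dermatitis that the investigator blames on the medium still counts as free of device irritation. The tolerability statement could then look clean while the adverse event table or the list of withdrawals shows skin reactions to a product that the instructions require with the device. A user of the device will experience the pair, so tolerability of the pair is what the study can and should report.

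**Working it through.** The plan gives no tolerability rate, threshold, denominator or expected irritation rate, and section 12.1 says only that the sponsor chose 50 subjects. There is no planned figure to reproduce, so the check is mainly a comparison of the text.

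**Can the design separate device from medium?**

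- Exposure: every subject gets both, on the same zones at the same session (sections 7.1.5, 10.1, 10.3, 10.6). There is no sham, medium-only or untreated group.
- Visit grading: sections 7.2.1 to 7.2.5 have the investigator grade redness, swelling, dryness and peeling from 0 to 4 as tolerability of the device. No item or rule assigns a sign to the medium.
- Adverse event causality: sections 11.2.2 and 12.4 rate and group events by relation to a single study product, so they do not supply the split.

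The endpoint therefore calls for an attribution that neither the design nor the data collection supports.

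**Would irritation from the medium be lost?** No.

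- The graded signs are recorded at every visit whatever their cause.
- Section 11.2 records adverse experiences whether or not they are attributed to the product, and section 12.4 summarizes all of them.
- Section 12.3 asks discontinuing subjects about both products, and section 9.1 has its own termination category for dermatitis.

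The gap lies in the wording of one endpoint.

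**How much could it move the endpoint?** Assume that the endpoint is reported as the percentage of all n = 50 subjects who are free of irritation. With k cases blamed on the medium and left out, the rate is overstated by k/n:

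- k = 1: 1/50 = 2 points
- k = 3: 3/50 = 6 points (with no other cases, 100% in place of 47/50 = 94%)
- k = 5: 5/50 = 10 points

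To see how readily such cases could arise, let q be the rate of irritation from the medium. The documents give no value, so a range is shown. The expected number of cases is 50q, and the chance of at least one is 1 − (1 − q)^50.

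| Assumed q | Expected cases | Chance of at least one |
|---|---|---|
| 1% | 0.5 | 39.5% |
| 2% | 1.0 | 63.6% |
| 5% | 2.5 | 92.3% |
| 10% | 5.0 | 99.5% |

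These are illustrations, not forecasts. They show that, because the endpoint is absence of irritation at any time, a single attribution decision can change the reported result.

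**The case against.** The strongest reply has four parts.

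- **Device use already includes the medium.** The synopsis lists it as an ancillary product, and the device instructions in the synopsis and section 10.2 make applying it one of the steps. This stands for efficacy: use of the device in section 12.5 can fairly be read as use with the medium. It is weaker for tolerability, because section 12.3 moves from products in the plural to the device alone within two sentences.
- **No one plans to exclude such cases.** The graded signs are labelled device tolerability without attribution, so irritation from either product would be scored there. This stands. Exclusion is something the wording permits, not a planned step. But the endpoint is not defined as a function of those scores, so they do not settle what counts.
- **The cases are reported elsewhere.** This stands in full. A reader might infer that irritation from the medium would disappear from the study. The documents do not support that, for the reasons shown in the working.
- **The endpoint has other gaps.** Irritation has no grade threshold and no rule for signs present at baseline, and subjects keep using their own moisturizer, cleanser and cosmetics. This is true, and the edit below does not supply a threshold or a baseline rule. It does remove the one attribution that the design cannot support.

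A reader might also infer that the efficacy result would credit direct current with a benefit that belongs to the medium. The documents do not show this. They give neither the composition of the medium nor any evidence that it acts on acne. The larger problem for efficacy is the lack of a concurrent control: change from baseline also contains natural course and regression to the mean, and the medium is one hypothetical part of that sum.

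**Conclusion.** The concern holds for the tolerability endpoint. Its wording in the synopsis and section 12.3 is narrower than the plan's own description of the study products and depends on an unblinded attribution that the design cannot support. The consequence is a possibly biased endpoint that may disagree with the adverse event summaries.

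The size is 2 percentage points per case left out, on the assumption that all 50 subjects are the denominator. The number of such cases cannot be derived from the documents, and no particular total, such as 94% against 100%, should be read as expected.

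For efficacy, only a minor point of consistency remains: the design evaluates the device used with the medium, and the objective and conclusion should say so. The documents support no stronger claim about the medium's effect on acne.

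**What to change.** **Main change.** In the synopsis (Endpoints) and section 12.3, define the tolerability endpoint as the absence of investigator-assessed skin irritation at any time in the 12 weeks during use of the study products (device and electroconductive medium), with no attribution to one or the other. This also brings the endpoint into line with the preceding sentence of section 12.3.

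**Matching edit.** In the synopsis objective, section 4 and section 12.5, refer to the device used with the supplied electroconductive medium. This states what was tested. It does not make up for the missing concurrent control, and no rewording can isolate the effect of the current.

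**Related inconsistency.** The synopsis describes a thin layer of medium in one place, while the numbered instructions there and in section 10.2 call for a liberal amount. These should be reconciled so that exposure to the medium is described consistently.

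**Cost.** Protocol wording only, with no new data, visits or subjects. Under section 14.5 a revision needs written approval from the sponsor and the IRB. The downside is a possibly less favourable tolerability result, by 2 points for each case newly counted on the assumption above, and a slightly narrower statement of what was shown.

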12.4 SAFETY ASSESSMENT

Incidence of all adverse events reported during the study will be summarized. Tabulated summaries will include adverse events grouped by relation to study product. The safety endpoint is the absence of significant adverse reactions.

12.5 EFFICACY ASSESSMENT

The efficacy endpoint is the investigator assessed improvement in investigator global assessment (IGA) after 12 weeks of every other day device use as compared to baseline.

13. ETHICS

13.1 INFORMED CONSENT

The principles of Informed Consent, according to FDA Regulations and ICH step 5 guidelines on GCPs, will be followed.

Subjects must provide written informed consent prior to any study procedures being completed. Each subject's signed informed consent must be kept on file by the Investigator for Regulatory Authorities' inspection at any time. A copy of the signed and dated consent form will be given to the subject.

13.2 INSTITUTIONAL REVIEW BOARD (IRB)

The study will be submitted to an IRB selected by Dermatology Consulting Services for approval to insure the safety of the human subjects enrolled in the study.

13.3 SUBJECT CONFIDENTIALITY

All participants are concerned for the individual subject's privacy and, therefore, only a subject identification number and subject initials will identify all subject data. However, in compliance with federal guidelines regarding the monitoring of clinical studies and in fulfillment of his/her obligations to the Sponsor, it is required that the Investigator permit the study monitor and/or FDA representative

to review that portion of the subject's medical record that is directly related to the study. This shall include all study relevant documentation including subject medical histories to verify eligibility, laboratory test result reports to verify transcription accuracy, admission/discharge summaries for hospital stays occurring while the subject is enrolled in the study, and autopsy reports for deaths occurring during the study.

As part of the required content of informed consent, the subject must be informed that his/her medical chart may be reviewed by the sponsor, the Sponsor's authorized representative, or a representative of the FDA. Should access to the medical record require a separate waiver or authorization, it is the investigator's responsibility to obtain such permission from the subject in writing before the subject is entered into the study. All subjects will sign a HIPAA document as part of the informed consent.

14. 14.1 INITIATION

DOCUMENTATION SITE DOCUMENTS REQUIRED FOR

Prior to the initiation of the study, the following items must be received:

- a) Sponsor approval of study
- b) Current curriculum vitae of the Investigators
- c) Copy of Principal Investigator's Medical license
- d) A signed copy of the protocol Investigator's Agreement page
- e) Original Non-Disclosure Agreement
- f) Signed Budget Agreement
- g) Approved FDA Investigational Device Exemption

14.2 SPONSOR

STUDY DOCUMENTS SUPPLIED BY THE

Dermatology Consulting Services will provide all study documents.

14.3 RECORDS

MAINTENANCE AND RETENTION OF

The study will be conducted according to Good Clinical Practices as outlined in ICH step 5 guidelines by the Food and Drug Administration. It is the responsibility of the Investigator to maintain a comprehensive and centralized filing system of all relevant documentation.

Investigators will be instructed to retain all study records required by the sponsor, as well as the regulations, in a secure and safe facility with limited access. Regulations require retention for a period of at least two years after last marketing approval and notification from the sponsor. These regulatory documents should be retained for a longer period if required by local regulatory requirements.

Archiving of data - Copies of all pertinent records will be retained by the investigator for at least two years following final approval of the drug and/or notification from the sponsor. These records include documents pertaining to the receipt and return of drug supplies, IRB, Informed Consent, as well as final signed case report forms. No documents shall be transferred from the site or destroyed without first notifying the sponsor. The sponsor will archive the data for the lifetime of the product.

14.3.1 CASE REPORT FORMS (CRF)

CRFs for individual subjects will be provided and completed by Dermatology Consulting Services, as appropriate. CRFs must be legible and complete.

A CRF must be completed and signed by the investigator for each subject enrolled, including those removed from the study for any reason. The reason for removal must be noted on the study conclusion CRF by the investigator for each subject. CRFs must be kept current to reflect the subject's status at each phase during the course of the study. Subjects are not to be identified on CRFs by name; appropriately coded identification and the subject's initials must be used. The investigator must keep a separate log of the subject's names and addresses.

The research site will maintain the following documents:

- 1. Subject Screening Log: This log will reflect the reason any subject screened for the study was found to be ineligible.
- 2. Study Personnel Signature Log: This log will contain all site personnel along with their responsibilities and signatures. This log will be maintained at the site throughout the study.
- 3. Monitoring Log: This log will contain the date and purpose of all monitoring visits by the Sponsor.
- 4. Enrollment Log: This log will contain subject initials and start and end dates for all subjects enrolled.
- 5. Product Inventory / Packing Slip Log: This log will reflect the total amount of study product shipped to the site and received and signed for by the Investigator.
- 6. Product Accountability Log: This log will reflect the total amount of study product dispensed to and returned by each subject.

14.3.2 MONITORING

A Sponsor appointed representative, if desired will monitor the study.

14.4

PRIMARY SOURCE DOCUMENTS

Dermatology Consulting Services will not maintain source documents for this study. Final case report forms (CRFs) will be maintained as study documentation.

14.5

PROTOCOL MODIFICATION

The procedures defined in the protocol and in the CRF will be carefully reviewed to ensure that all parties involved with the study fully understand the protocol. In order to ensure the validity of the data, no deviations from the protocol may be made unless the issue is broad enough to warrant revision of the protocol. Such revisions must be submitted to and have approval in writing from the Sponsor and the IRB prior to implementation.

14.6

AUDITS/INSPECTIONS

During the course of the study and/or after it has been completed, one or more site visits may be undertaken by auditors as authorized representatives of the Sponsor.

